10.2 Planned recruitment rate

Development of tool - 65 operations.

Validation of tool – 100 operations

10.3 Statistical analysis plan

10.3.1 Summary of baseline data and flow of patients

Data to be analysed includes:

- Heart rate
- Motion tracking data from XSens DOT
- Questionnaires completed
- Semi structured Interviews
- Information from medical records including (BMI, waist/hip measurements and ratio)

10.3.2 Primary outcome analysis

Multi-variate analysis will be performed to identify factors increasing surgeon impact and statistical modelling will be used to calculate a single value that is representative of the cumulative 'impact' of the case on the surgeon so that cases can be categorised as 'high', 'intermediate' or 'low' impact. Case complexity (for example BMI, previous surgery) and subjective surgeon opinion will be compared with the impact classification to determine internal consistency (Cronbach alpha) and content validity.

Following the development of the impact classification, geographical external validation will be conducted at additional sites, and surgeons recruited to confirm the accuracy of the 5-point assessment tool.

Data gathered from the interviews will undergo qualitative analysis

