3. RESEARCH QUESTION /OBJECTIVES AND OUTCOME MEASURES/ENDPOINTS

Hypothesis: The physical/psychological impact on surgeons is less with RA compared to SS and open surgery.

Aim: To develop and validate a 5-point assessment tool to objectively measure both the physical and psychological impact of complex surgical cases on a surgeon

in order to give a single categorisation of impact: high, intermediate or low.

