3.2 Secondary objectives

- 1. Analysis to combine the 4 variables to give a single value of 'impact' (high/intermediate/low) per procedure
- 2. Validation of the combined impact values (subjective vs objective assessment)
- To analyse the impact of providing surgical training and supervision to surgical traineeswith varying levels of experience within a live surgical setting using heart rate monitoring as objective measures (if the case has been deemed suitable by the Consultant for the trainee)
- 4. Willingness of recruitment of patients/surgeons and sample size calculations for a future multi-centre study
- 5. Identification of primary/secondary outcomes for a future definitive multi-centre study

- 6. Optimisation/validation of patient data recording measures to capture anaesthetic/operative/clinical events and outcomes
- 7. Safety assessment of measurement tools and recording devices in the theatre environment
- 8. Optimisation of surgeon continuous heart rate monitoring during procedure, data collection and analysis
- 9. Optimisation of positioning and recording of muscle movement/activity sensors and streamlining of data-analysis
- 10. Optimisation/validation of WMS and State Trait Anxiety Inventory (STAI) questionnaires and data analysis
- 11. To include the analysis of the cortisol samples collected at the feasibility stage within the preliminary analysis

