3.3 Outcome measures/endpoints

To design and validate a 4-point assessment tool that can objectively measure the physical and psychological impact of complex surgical cases on a surgeon. The tool will then be taken forward and used in a large, multi-centre trial to determine whether a difference in surgeon impact exists between the different surgical modalities (open/laparoscopic/robotic) and if so to quantify the magnitude of the difference.

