10 STATISTICS AND DATA ANALYSIS

10.1 Sample size calculation

A key unknown for the feasibility of the full trial is whether it is possible to capture all 5 components of the tool for objective assessing stress of surgery therefore the proportion of surgeries with all 5 variables completely captured will be our primary feasibility outcome.

We believe this will be high, at around at least 90%. A sample size of 65 produces a two-sided 95% confidence interval with a width equal to 0.16 when the sample proportion is 0.90, with lower limit 0.80 and upper limit 0.96. This data will be used to determine the parameters to classify cases into low, intermediate and high impact depending on the physical/psychological impact on the surgeon.

A further 100 cases have been included as validation of the tool. This is based on a 50% prevalence of 'high' impact procedure and 95% confidence level and a sensitivity of 0.90 (0.772-0.970).

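### Validation is stated only for the high/intermediate/low class; the continuous impact value calculated first has no clearly planned validation, although the tool is meant to quantify differences between surgical routes

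*Protocol*

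**What the plan says.** Section 3 gives the aim as a tool that measures impact "in order to give a single categorisation of impact: high, intermediate or low". Secondary objective 1 in section 3.2 is worded "Analysis to combine the 4 variables to give a single value of 'impact' (high/intermediate/low) per procedure", and objective 2 is to validate the combined impact values, subjective against objective.

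Section 10.3.2 sets out the order of work. Statistical modelling is to "calculate a single value that is representative of the cumulative 'impact' of the case on the surgeon so that cases can be categorised" into the three levels. After that, case complexity (BMI and previous surgery are the examples) and "subjective surgeon opinion will be compared with the impact classification to determine internal consistency (Cronbach alpha) and content validity". External validation at further sites follows once the classification has been developed.

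Section 10.1 says the feasibility data (65 cases) will supply the parameters for classifying cases. It adds 100 validation cases and explains the number: "This is based on a 50% prevalence of 'high' impact procedure", with 95% confidence and a sensitivity of 0.90 (0.772-0.970).

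On later use, section 3.3 says the tool will go into a large multi-centre trial to find whether surgeon impact differs between open, laparoscopic and robotic surgery and "if so to quantify the magnitude of the difference". Objective 4 in section 3.2 has this study supply "sample size calculations for a future multi-centre study".

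**The concern.** The inputs to the score are continuous or ordinal: heart rate, movement, STAI, and a WMS questionnaire that now carries a numerical pain score. Section 10.3.2 combines them into one value and cuts that value into three levels. The stated comparison with complexity and surgeon opinion then uses the cut version. Section 10.1 goes down to two levels for sizing.

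Cutting a graded score treats all cases within a class as equal and cases on either side of a cut-off as different. Here the cut-offs will come from 65 cases. A modest association with BMI or with the surgeon's rating is then estimated less precisely than the collected data allow.

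There is also a mismatch with purpose. The later trial is meant to put a size on the difference between routes. If only the class has been validated, that trial must either express the difference in classes, which is coarse, or use the underlying value, for which this protocol plans no clear validation.

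**Working it through.** **The plan's own validation figure.** 100 cases at 50% prevalence give 50 'high' cases, and a sensitivity of 0.90 is 45/50. The exact (Clopper-Pearson) 95% interval is 0.782 to 0.967, against the stated 0.772 to 0.970. The stated limits match the exact interval at about 44 'high' cases. The gap is about one percentage point at the lower limit and does not affect this point. What matters is that the figure is the precision of a two-level sensitivity. The protocol gives no test, correlation or power for validation.

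**Inputs for the illustration.**
- N = 100 validation cases (section 10.1).
- 50% 'high' (section 10.1).
- Three classes (sections 3 and 10.3.2). Their proportions are not stated, so two splits are shown: equal thirds, and 50% 'high' with 25% in each other class.
- Assumed, not in the protocol: correlation r between the value and the comparator, bivariate normality, independent cases, two-sided 5% test. Repeated procedures by the same surgeon are ignored.

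**Step 1: how far each cut shrinks a correlation.** With φ the standard normal density and equally spaced class scores, the factor f is the correlation between the score and its cut version.
- 'High' versus not at 50%: φ(0)/√0.25 = 0.3989/0.5 = 0.798.
- Equal thirds: 2φ(0.431)/√(2/3) = 0.7272/0.8165 = 0.891.
- 50/25/25, scored 2/1/0: variance = 0.25×1 + 0.50×4 − 1.25² = 0.6875, so f = (φ(0.674) + φ(0))/√0.6875 = 0.7167/0.8292 = 0.864.

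**Step 2: power by Fisher's z.** Power ≈ Φ(atanh(r·f)·√(N−3) − 1.96), with √97 = 9.849. At r = 0.30:
- full value: 0.3095×9.849 − 1.96 = 1.088, power 86.2%
- thirds: atanh(0.2672) = 0.2739, power 76.9%
- 50/25/25: atanh(0.2593) = 0.2654, power 74.3%
- 'high' versus not: atanh(0.2394) = 0.2441, power 67.2%

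Simulation with 20,000 data sets at r = 0.30 gave 86.8% (full), 78.1% (thirds) and 67.7% ('high' versus not).

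**Step 3: range over r (N = 100).**

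| r | Full value | Thirds | 50/25/25 | 'High' v not | Loss, points |
|---|---|---|---|---|---|
| 0.20 | 51.5% | 42.6% | 40.5% | 35.4% | 9 to 16 |
| 0.25 | 71.1% | 60.7% | 58.0% | 51.3% | 10 to 20 |
| 0.30 | 86.2% | 76.9% | 74.3% | 67.2% | 9 to 19 |
| 0.35 | 94.9% | 88.8% | 86.8% | 80.7% | 6 to 14 |
| 0.40 | 98.7% | 95.6% | 94.4% | 90.3% | 3 to 8 |
| 0.50 | 100.0% | 99.7% | 99.5% | 98.6% | 0 to 1 |

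In the last column the smaller figure is for thirds and the larger for 'high' versus not.

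**Step 4: cost in cases.** For weak associations the required N scales with 1/f²: 1/0.891² = 1.26, 1/0.864² = 1.34 and 1/0.798² = 1.57, that is 26%, 34% and 57% more cases. As a check, 80% power at r = 0.30 needs 85 cases with the full value, 108 with thirds, 115 with 50/25/25 and 135 with 'high' versus not.

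**The case against.** The strongest reply is that the classification is the product. Section 3 and objective 1 both ask for a category, so analysing the category is not a shortcut. That stands, and the continuous analysis belongs beside the class, not in place of it.

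Second, the power figures belong to a test that the plan does not make. Validation is sized on the precision of a sensitivity, and section 10.3.2 names Cronbach alpha and content validity. A planned sensitivity of 0.90 also implies a strong relation. In a bivariate normal model at 50% prevalence, the underlying correlation would be about 0.95 if specificity were 0.90, and about 0.68 if it were 0.50 (both specificities are assumptions). At such values no cut loses any appreciable power. This also stands: correlations of 0.20 to 0.35 fit a weaker correlate, as BMI may prove to be, better than they fit the planned sensitivity. A reader might infer that the plan falls 9 to 19 points short of its power. The protocol sets no power target to miss, and that span is one assumed correlation across two different cuts.

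Third, a reader might infer that a class cannot quantify a difference between routes. It can, through a difference in the proportion 'high' or an ordinal odds ratio. Nor does objective 4 commit the later trial to sizing on the class.

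Fourth, some wording is open. Objective 2 speaks of impact values, section 10.3.2 begins with a multivariate analysis of factors that raise impact, and the secondary analysis of ergonomic data mentions no cut. These soften the point but do not remove it. Objective 1 glosses its single value as the three levels, and the only comparison with complexity and surgeon opinion spelled out in section 10.3.2 is with the classification. An unseen analysis plan might add the uncut value, but this protocol has already named the scale.

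**Conclusion.** The point holds as a mismatch between the analysis scale and the purpose. The protocol calculates a graded value, states its comparison with complexity and surgeon opinion only for the cut version, and expects the tool later to measure the magnitude of a difference. No section clearly plans validation of the uncut value.

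The size depends on the strength of association, which the protocol does not give. Under the stated assumptions the loss matters for weak to modest correlations and is negligible from about 0.50 upward. The extra-case figures of 26%, 34% and 57% hold for weak associations. They would carry into the multi-centre study only if that study were sized on a class cut in the same way. Clustering by surgeon would change the absolute power figures. The documents do not support calling the validation stage underpowered or the tool incapable of quantification. They do support adding an analysis of the value already being calculated.

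**What to change.** In section 10.3.2:
- Fix both the scoring formula and the cut-offs on the feasibility cases, and apply them unchanged to the 100 validation cases.
- Keep the planned classification and its sensitivity as the stated aim.
- Alongside it, relate the continuous impact value to BMI and other complexity measures and to the surgeon's rating, by correlation or regression with 95% confidence intervals.
- Report the mean and SD of the continuous value, so that objective 4 can size the multi-centre study on that scale and section 3.3's purpose can be met.

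The cost is a change of wording, a little extra analysis and two scales to report, of which the continuous one is less immediately readable. It needs no new data, visits or procedures.

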7.6 Trial assessments/procedures

Surgeons

Pre-study assessment will be conducted as detailed in section 5 prior to surgery.

The LapAR (Inovus) comes with its own established system of data capture and analysis that provides objective and comparable metrics when the surgeon undertakes different simulated tasks. The software will include both general surgical and gynaecological relevant exercises. The data obtained will be used to establish that the sensors and heart rate monitor will not have a negative impact on the surgical tasks itself in the live setting.

Day of surgery

A member of research team will meet with the surgeon (this will be arranged in advanced so that it does not coincide with clinical processes) for the following assessments:

Before surgery:

- Completion of the questionnaire which will take about 10 minutes to complete
- Wearing of sensors

After surgery:

Completion of the questionnaire which will take about 10 minutes to complete

Surgeons will be invited to participate in an interview with the researcher to discuss their experience of the measurement tool and challenges they have experienced when collecting the data. This will be two interviews per participant to gather their views on the various aspects of the study as a whole as well as their potential ongoing musculoskeletal symptoms.

Patients

Access to medical records to obtain data:

- Medical co-morbidities
- Body habitus (BMI)
- Intra/post-operative events/recovery
- Waist/hip measurements will be taken by the researcher on the morning of surgery.
- Subjective assessment from the patient's healthcare professional regarding the level of complexity of the procedure.

There are no research trial specific assessments for patients but consent will be sought to access their medical records to obtain data from their medical records. The data collected will be pseudonymised at the site before being transferred to the University of Leicester. There will be no personal data being transferred.

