11. DATA MANAGEMENT

11.1 Data collection tools and source document identification

Surgeons

- Demographic information
- State Trait Anxiety Inventory and modified Nordic Work-related musculoskeletal Symptoms questionnaires.
- Data from sensors XSENS DOT and Actiheart heart rate monitor
- Interviews will be recorded on an encrypted voice recorder and we will state the
 participant's number at the beginning of the recording so that they are not identifiable.
 The recording will then be transferred to the University of Leicester and will be deleted
 from the recorder. The recording will be transcribed by the researcher or by a

transcribing company. If a transcribing company is to be used, there will be confidentiality agreement in place with the company.

Patients

Access to medical records to obtain data:

- Medical co-morbidities
- Body habitus (BMI, waist-hip measurements and ratio)
- Intraoperative events
- Subjective assessment from the patient's surgeon regarding the level of complexity of the procedure.

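### The 100 validation procedures are sized on sensitivity for 'high' impact, but the stated analysis estimates no accuracy measure and no reference defines a truly 'high' case

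*Protocol*

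**What the plan says.** Protocol section 10.1 introduces the validation stage with "A further 100 cases have been included as validation of the tool" and gives its basis: "This is based on a 50% prevalence of 'high' impact procedure and 95% confidence level and a sensitivity of 0.90", with an interval of 0.772 to 0.970.

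Section 10.3.2 describes how a single impact value is derived and cut into three classes. It continues: "Case complexity (for example BMI, previous surgery) and subjective surgeon opinion will be compared with the impact classification". The rest of that sentence gives the purpose, which is Cronbach alpha for internal consistency, and content validity. The next paragraph moves to external validation at further sites, with "surgeons recruited to confirm the accuracy of the 5-point assessment tool". It names no comparator and no accuracy statistic.

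Objective 2 in section 3.2 reads "Validation of the combined impact values (subjective vs objective assessment" (closing bracket omitted here). It names no instrument, rater or threshold.

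The one subjective item collected is a complexity rating. Section 7.6 describes it as "Subjective assessment from the patient's healthcare professional regarding the level of complexity of the procedure" and section 11.1 as "Subjective assessment from the patient's surgeon regarding the level of complexity of the procedure". The schedule of procedures in section 7 lists it under surgeons, after the operation.

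**The concern.** Sensitivity is the share of truly 'high' cases that the tool also calls 'high'. Both that figure and the 50% prevalence need a definition of 'high' that comes from outside the tool. The protocol uses both numbers to size the stage and supplies no such definition. It also does not say whether 'intermediate' counts with 'high' or with 'low' when three classes are reduced to two.

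The stated analyses do not fill the gap. Cronbach alpha describes how far items vary together. Content validity concerns whether the tool covers the right ground. Either could look satisfactory in a tool that misclassifies many procedures.

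At stake is the claim carried forward. Section 2 says the outcome of the study will be a validated tool for a prospective multi-centre comparison of open, laparoscopic and robotic surgery, and section 3.3 says the same of the tool's future use. As written, that claim would rest on no accuracy estimate.

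**Working it through.** **Inputs.** From section 10.1: 100 validation procedures, 50% 'high', sensitivity 0.90, 95% confidence, stated interval 0.772 to 0.970. From section 10.3.2: three classes, Cronbach alpha and content validity. The protocol gives no share of 'high' cases for any named reference and no error rate for any reference, so the values used for these in steps 3 and 4 are assumptions.

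**1. The plan's own figure.** Expected 'high' cases = 100 × 0.50 = 50, and 0.90 × 50 = 45. The exact (Clopper-Pearson) limits are the 2.5% point of Beta(x, n − x + 1) and the 97.5% point of Beta(x + 1, n − x). With x = 45 and n = 50 they are 0.782 and 0.967. The same method at n = 65 (x = 0.90 × 65 = 58.5) gives 0.800 to 0.961, which agrees with the feasibility interval in section 10.1. The stated 0.772 to 0.970 is not reproduced exactly at n = 50 by this method, nor by Wald, Wilson (with or without continuity correction), Agresti-Coull or Jeffreys. The exact method gives it at about 44 'high' cases. Each stated limit is within 0.01 of the exact result for 50, so this is minor and separate. It does confirm that the sizing is a precision statement about sensitivity among reference-positive cases.

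**2. Sizing against analysis.**

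- Quantity sized for (10.1): sensitivity for 'high'.
- Quantities analysed (10.3.2): Cronbach alpha and content validity.
- Claim made (10.3.2): accuracy confirmed.
- Reference for a truly 'high' case: none in 3.2, 7.6, 10.1, 10.3.2 or 11.1.
- Rule for 'intermediate': none.

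The first and third items need an estimate that the second does not provide.

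**3. Precision depends on the reference.** Hold the observed sensitivity at 0.90 and let the reference call a different share of the 100 cases 'high' (exact limits):

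- 50% (n = 50): 0.782 to 0.967, width 0.185
- 40% (n = 40): 0.763 to 0.972, width 0.209
- 33% (n = 33.3): 0.746 to 0.976, width 0.230
- 20% (n = 20): 0.683 to 0.988, width 0.305

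**4. The estimate depends on the reference.** Assume that the tool has sensitivity and specificity 0.90 against true impact, that true prevalence is 0.50, that the reference has sensitivity and specificity both equal to r, and that the errors of tool and reference are independent. The share the reference calls 'high' is then 0.5r + 0.5(1 − r) = 0.5, and

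apparent sensitivity = [0.5 × r × 0.90 + 0.5 × (1 − r) × 0.10] / 0.5.

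For r = 0.80 this is (0.36 + 0.01) / 0.5 = 0.74. For r = 1.00, 0.95, 0.90 and 0.70 it is 0.90, 0.86, 0.82 and 0.66. The same tool on the same number of cases can therefore show an expected sensitivity anywhere from 0.66 to 0.90, depending on how well the reference captures impact.

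**The case against.** The strongest reply is that this is a feasibility study. Its primary outcome is complete capture of the tool's components (sections 3.1 and 3.4), validation is a secondary objective, and cut-offs and the order of validity analyses are commonly left to a statistical analysis plan, which is not shown here. Part of this stands: the primary outcome is untouched, and a cut-off alone could be left to that plan. But section 10.3 prescribes validation statistics that do not match the protocol's own sizing, and the 50% and 0.90 in section 10.1 have no meaning without a reference. That is a mismatch between two stated sections.

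A second reply is that objective 2 already points to a subjective reference. It does, and the fix follows it. It fixes no instrument, rater or threshold, however, and the only subjective item described rates the complexity of the procedure, not impact on the surgeon.

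Two stronger readings are tempting and are not supported. A reader might infer that BMI, previous surgery and surgeon opinion are rival references from which the most favourable could be picked, and might calculate how far that raises the chance of reaching 45/50. The comparators are offered for consistency and content validity, BMI and previous surgery are examples of one comparator (case complexity), and no pass mark is set. Such a probability would describe a decision rule that the protocol does not contain. A reader might also infer that sections 7.6 and 11.1 contradict each other on the rater. A surgeon is a healthcare professional, and the schedule of procedures and section 10.3.2 both point to the surgeon, so this is loose wording.

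**Conclusion.** The point holds as a mismatch between sizing and analysis. The 100 procedures are justified by a sensitivity of 0.90 at 50% prevalence. The analysis in section 10.3.2 does not estimate sensitivity, no reference makes a case truly 'high', and 'intermediate' has no place in a binary measure. The promised confirmation of accuracy therefore has no estimate behind it.

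The mismatch itself rests on the text alone. The size of the effect is illustrative: the width of the interval at 0.90 goes from 0.185 to 0.305 if the assumed share of 'high' cases falls from 50% to 20%, and the expected sensitivity of the same tool goes from 0.90 to 0.66 if the assumed accuracy of the reference falls from 1.00 to 0.70 with independent errors. This should be corrected before the validation data are seen. It does not affect the 65-procedure feasibility outcome.

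**What to change.** In section 10.3.2, state that the deciding validation analysis is the sensitivity and specificity of the 'high' class (high versus intermediate or low) in the 100 validation procedures, each with an exact 95% interval, against one reference named before those data are seen.

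In line with objective 2, make that reference the operating surgeon's post-operative subjective rating, worded to rate impact on the surgeon and not only case complexity. Fix its 'high' cut-off from the 65 development procedures, and record each rating before the tool's class is calculated. Keep BMI, previous surgery and rated complexity as supportive construct-validity associations. Use 'surgeon' in both 7.6 and 11.1.

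Cost: a small change to an item already in the schedule, made through the amendment route in Appendix 1. Section 4 shows that the feasibility stage had already produced data by this version, so the reworded item may be missing from some development cases. If so, the protocol should say which cases set the cut-off. The accuracy claim will rest on one imperfect subjective reference. Two of the tool's four components are the surgeon's own questionnaires, so the errors of tool and reference may not be independent and agreement may look better than it is. The report should say so.

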3.1 Primary objective

The proportion of surgical procedures where all 4 variables of the assessment tool are captured (continuous HR monitoring; continuous movement sensor monitoring; STAI questionnaire; WMS questionnaire).

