4. TRIAL DESIGN

This is an observational study with the aim of investigating the impact that open and minimally invasive surgery (including robotic assist and straight stick laparoscopy) can have on surgeons' physical and psychological health.

The study will be using a monitoring tracking equipment called XSENS DOT Sensors, Actiheart heart rate monitor which are CE marked and will be used in its licensed indication. All equipment being used within the UHL operating theatres for the purpose of the study will have approval/authorisation from the medical physics department. The data collected will be downloaded on to a tablet using Bluetooth technology. Cortisol measurements were initially obtained at baseline (for each surgeon), preoperatively /intraoperatively (at time of the removal of specimen) and postoperatively as a biomarker to measure the cognitive impact of surgery. However, process evaluation within the feasibility stage has revealed it to be inconvenient and a potential disruption to theatre workflow especially if more than one case is recruited per list. The cortisol measurements obtained thus far will be included in the preliminary analysis but this biomarker will be omitted in the data collected at the validation stage. Surgeons will be expected to complete the STAI and modified Nordic WMS questionnaires as well. The WMS questionnaires have been further modified following the process evaluation carried out throughout the feasibility stage – to now include a numerical pain score to further objectively evaluate the intensity of the work related injuries sustained/ experienced.

XSENS DOT

ACTIHEART HEART RATE MONITOR

The research involves working in collaboration with the wearable robotics team at Loughborough University.

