7. TRIAL PROCEDURES

Schedule of Procedures

Procedures	Visits (insert visit numbers as appropriate			Visits (insert visit numbers as appropriate)			
	Screening	Baseline	Visit 1 (before the operation)	Pre- Op	During Op	After Op	Follow Up & post interview
Surgeons:							
Approached by Research team	х						
Informed consent		Х					
Attendance at Leicester University			х				

 Monitoring of the equipment Laparoscopic simulator tasks Feedback on questionnaires Semi structured interview 						
Subjective assessment about the complexity of the procedure					Х	
Sensor monitoring				х		
Pre-op questionnaire			х			
Post-op questionnaire					х	
Interview						X2
Patients:						
Eligibility check	х					
Informed consent		х				
Information collected from medical records		х	х		х	

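### Cronbach alpha and content validity are the wrong summary for comparing the impact class with case complexity and surgeon opinion, and because the score contains the surgeon's own questionnaires the planned check is not subjective versus objective

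*Protocol*

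**What the plan says.** The tool's four components are listed in Protocol section 3.1: "continuous HR monitoring; continuous movement sensor monitoring; STAI questionnaire; WMS questionnaire". Section 4 states who fills in the two questionnaires: "Surgeons will be expected to complete the STAI and modified Nordic WMS questionnaires as well". Section 3.2 then plans "Analysis to combine the 4 variables to give a single value of 'impact' (high/intermediate/low) per procedure" and, as the next objective, "Validation of the combined impact values (subjective vs objective assessment".

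Section 10.3.2 names the comparators, "Case complexity (for example BMI, previous surgery) and subjective surgeon opinion", and says that they "will be compared with the impact classification to determine internal consistency (Cronbach alpha) and content validity". It names no measure of class agreement and no comparison that uses the sensor data alone. Its next paragraph adds external validation of accuracy at further sites, and section 10.1 sizes the 100 validation cases on a sensitivity of 0.90 for high-impact procedures.

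The case-level opinion that is listed for collection concerns complexity. The section 7 schedule lists, among the surgeon procedures, "Subjective assessment about the complexity of the procedure". Section 11.1 has "Subjective assessment from the patient's surgeon regarding the level of complexity of the procedure". Section 7.6 assigns the same item to the patient's healthcare professional.

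**The concern.** There are two separate problems.

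**The statistic and its label.** Alpha asks whether the items of one scale vary together. It is unaffected by a constant shift between two ratings, so a tool that places cases in the wrong class can still score well. The product here is a class (high, intermediate or low), so class agreement is what matters. Content validity concerns whether a tool's items cover the construct. Comparing the resulting class with an external rating is convergent validity.

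**The contrast.** Section 3.2 describes the validation as subjective against objective, but two of the four inputs to the combined value are the surgeon's own answers. If the opinion comes from the same surgeon, score and comparator share a rater and a method. Some association would then be expected even if heart rate and movement carried no information, and the plan contains no analysis that would show this.

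Sections 2 and 3.3 intend the tool for a multi-centre comparison of open, laparoscopic and robotic surgery. It matters there whether the sensors or the questionnaires drive the score.

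**Working it through.** The plan gives no figure for alpha, so there is none to reproduce. Its one validation figure, sensitivity 0.90 (0.772 to 0.970) in section 10.1, does not enter this check.

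**1. Can alpha be high when classes disagree?**

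Inputs: 100 cases (section 10.1). Assumed: the comparator splits 33 low, 34 intermediate, 33 high, scored 0, 1, 2, and the tool rates every low or intermediate case one class higher. The tool then gives 0 low, 33 intermediate, 67 high.

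- Comparator variance = (33 + 33)/99 = 0.667.
- Tool mean = 1.67; variance = (33 × 0.67² + 67 × 0.33²)/99 = 0.223.
- Covariance = (33 × 0.67 + 33 × 0.33)/99 = 0.333.
- Variance of the sum = 0.667 + 0.223 + 2 × 0.333 = 1.557.
- Alpha = 2 × (1 − 0.890/1.557) = **0.86**.
- Exact agreement = 33/100 = **33%**.
- Chance agreement = 0.33 × 0 + 0.34 × 0.33 + 0.33 × 0.67 = 0.333, so unweighted kappa = (0.330 − 0.333)/(1 − 0.333) = −0.005.
- Linear weights: observed disagreement 0.67 × 0.5 = 0.335, expected 0.444; kappa = 1 − 0.335/0.444 = **0.25**.
- Quadratic weights: observed 0.1675, expected 0.3325; kappa = 0.50.
- For 'high': sensitivity 33/33 = 1.00, specificity 33/67 = 0.49.
- Spearman correlation = 0.86.

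In this example Spearman and sensitivity miss the error, as alpha does. The cross-table, linear-weighted kappa and specificity show it. Quadratic weighting partly hides it, so the weights must be named in advance.

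In the limiting case, where the tool says low or intermediate whenever the surgeon says intermediate or high, half of the cases each, alpha is 1.00 with 0% agreement and kappa −0.33.

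**2. What can the shared self-report produce on its own?**

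Assumptions, none given in the protocol: four standardised components with equal weights; heart rate and movement independent of everything else; STAI and WMS each correlating r0 with the surgeon's opinion and related to each other only through it (mutual correlation r0²).

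- Score against opinion: r = 2·r0/√(4 + 2·r0²).
 - r0 = 0.5: 1.0/√4.50 = **0.47**.
 - r0 = 0.6: 1.2/√4.72 = **0.55**.
- Two-item standardised alpha = 2r/(1 + r): **0.64** and **0.71**.
- AUC for an opinion above its median, under bivariate normality: 0.716 and 0.755.
- Sensors alone: r = 0, AUC **0.50**.
- Questionnaires alone: r = 2·r0/√(2 + 2·r0²) = 1.0/√2.50 = 0.63 and 1.2/√2.72 = 0.73. Here the combined score does worse than its own questionnaires.

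Varying the assumptions: if STAI and WMS correlate r0 with each other as well, r becomes 2·r0/√(4 + 2·r0) = 0.45 and 0.53, with alpha 0.62 and 0.69. Simulated with all three self-report measures correlating 0.7 or 0.8, alpha is 0.75 or 0.81, while kappa for tertile classes is only 0.30 or 0.36.

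**The case against.** Several points on the other side are fair.

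- **Alpha is not the whole validation plan.** Sections 10.1 and 10.3.2 also plan sensitivity for high impact and external validation at further sites. This stands, and a reader should not infer that validation rests on alpha alone. These plans do not correct the sentence at issue, though: neither names the reference against which accuracy would be judged.
- **One comparator is patient data.** BMI and previous surgery share no rater with the score. A reader might infer that this check is circular too, because section 10.3.2 looks for factors that increase impact. The documents do not support that: sections 3.1 and 3.2 list four components, and neither BMI nor previous surgery is among them.
- **The listed opinion is about complexity, not felt impact, and section 7.6 may assign it to someone else.** This stands as a limit on the second problem. Complexity may correlate with STAI and WMS less than assumed above, and the inflation would then be smaller. Section 10.3.2 itself says surgeon opinion, and section 11.1 names the patient's surgeon.
- **Self-report is in the tool on purpose.** Section 1 explains why stress measurement needs it. The concern is with how the combined value is checked, not with including the questionnaires.
- **The one-class-shift example is extreme.** It is: that tool never uses the low class. It shows what alpha cannot detect, not what is expected to happen.
- **A separate analysis plan may add better statistics.** It may, but the protocol already fixes alpha and the type of validity, so this is a wrong choice rather than an omission.

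**Conclusion.** The point holds in two parts. Alpha and content validity are wrong for the comparison in section 10.3.2; this rests on what alpha measures and needs no assumption about the data. The example gives 0.86 with 33% exact agreement and linear-weighted kappa 0.25. The comparison of the combined value with surgeon opinion is also not the subjective-versus-objective contrast of section 3.2, because the score includes two questionnaires that the surgeon completes.

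The size of the second effect is not known. Under the stated assumptions (opinion from the same surgeon, correlations of 0.5 to 0.6, equal weights, uninformative sensors) alpha is 0.64 to 0.71 and AUC about 0.72 to 0.76. That is moderate. A reader might infer that the plan will declare a valid tool when the sensors add nothing; the documents support only that the planned analysis could not tell.

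Despite the heading of section 10.3.2, combining and validating the score are secondary objectives. The primary endpoint, the proportion of cases with all components captured, is untouched. This should be fixed, but it does not threaten the feasibility result.

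**What to change.** 1. In section 10.3.2, for the comparison with surgeon opinion, replace alpha with the three-class cross-table and linear-weighted kappa, plus sensitivity and specificity for 'high'. Use confidence intervals that allow for several procedures by the same surgeon. Keep alpha only for items or components inside the score. Kappa needs the opinion recorded in the same three classes, and the protocol does not state its scale. BMI and previous surgery have no such classes and can be tabulated by impact class.
2. Call the comparison convergent validity.
3. Also compare a sensor-only sub-score (heart rate and movement) with the surgeon's opinion, and report what the combined score gains over the questionnaires alone. The sensor-only comparison is the contrast that section 3.2 describes.
4. State whether the opinion concerns complexity or impact, and reconcile sections 7.6 and 11.1 on who gives it.

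The cost is a wording change and a few extra tables from data already planned. If the opinion is not already recorded in three classes, one item is added to the post-operative form. No further cases are needed.
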